There is a sigmoid progression of clinical impairment and deficits over time. A preclinical stage without apparent functional impairment or clinical features might be a phase when pathological changes are starting to accumulate without apparent deficits. This phase is followed by a stage of evolving early disease, which is clinically non-specific and escapes current consensus criteria. A phase with steep progression follows; captured by current consensus criteria, this phase represents patients diagnosed at an early stage who fulfil the possible or probable MSA criteria by having a low Unified Multiple System Atrophy Rating Scale (UMSARS) score. Finally, patients reach a late plateau phase that almost invariably meets the consensus criteria for probable MSA.

No disease-modifying therapies are currently available. The management of the disease involves purely symptomatic treatments, that is, medications to stabilize and raise blood pressure and medications, such as levodopa, to reduce Parkinson's disease-like signs and symptoms. However, only a subset of MSA patients benefit from levodopa. Dopamine-agonists are not considered a therapeutic option due to poor efficacy and risk of worsening orthostatic hypotension. There are no therapies that can slow down disease progression by inhibiting the neurodegenerative processes leading to neuronal cell loss. Thus,

due to the fatality and lack of effective treatments, there is an unmet need for a treatment that can delay the progression in MSA.

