14.3 Analysis Methodology for the Primary Endpoint

14.3.1 Primary Analysis of the Primary Endpoint

The primary efficacy analysis following up to 72 weeks of treatment will be based on a Bayesian repeated measures model, also referred to as a Bayesian functional-impairment

progression model (BFPM), of the changes from baseline in the UMSARS TS. The BFPM incorporates the following aspects:

- Repeated measures for the change from baseline in the UMSARS TS score over the recurring 72-week's visit schedule
- Piece-wise linear rate of progression per 12-week time interval. However, does not require equally spaced intervals between observations. Time modelled continuously
- Patient-level random effect in rate of progression
- Proportional treatment effect, θ, for slowing of disease progression rate when treated relative to placebo. In particular, if θ<1, the active treatment slows the rate of progression relative to placebo. If θ>1, the active treatment increases the rate of progression relative to placebo. If θ=1, the rate of progression of UMSARS TS is the same for both active treatment and placebo
- Fixed multiplicative covariate effects in the increase or decrease in the overall rate of
 progression of UMSARS TS for categorized CCI

and region (US and Japan) common across all visits

- Prior distributions for model parameters selected in a conservative and non-informative manner using relatively large outcome spaces
- The primary analysis considers only actual observations and does not impute missing data

Let change from baseline in the UMSARS TS at visit *j* for subject *i* be labelled $Y_{i,j}$, $i = 1, ..., N, j = 1, ..., J_i$ where there are J_i total post-baseline visits for subject *i*. Change from baseline will be modelled as piece-wise linear with time intervals, k = 1, ..., K, defined every 12 weeks. Let $X_{i,j,k}$ be the exposure (time since baseline in weeks) for subject *i* at visit *j* during the time interval *k*. The MSA progression model is:

$$Y_{i,j} \sim N(\mu_{i,j}, \sigma_{t(i)}^2); i = 1, ..., N; j = 1, ..., J_i$$

$$\mu_{i,j} = 0 + \sum_{k=1:K} \left(\beta_k + \beta_{k,i} \right) * (X_{i,j,k}/12) * \theta_{t(i)} * \exp\left(\delta_{g(i)} + \eta_{r(i)} \right)$$

where each parameter is defined below and the prior distribution for the parameter is given:

 β_k : Mean expected change from baseline over each 12-week interval

$$\beta_k \sim Norm(0, 10^2)$$
; $k = 1, \dots, K$

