 $\beta_{k,i}$: Subject-level additive random effect in change from baseline over each 12-week interval for subject *i*

$$\beta_{k,i} = \beta_i; \ \beta_i \sim Norm(0, \sigma_\beta^2); \ \sigma_\beta \sim Unif(0, 20)$$

Study 18331A – Statistical Analysis Plan

 θ_t : Multiplicative proportional slowing in rate of progression for treated (t=2) relative to placebo (*t*=1).

$$\theta_1 = 1; \ \theta_2 \sim Unif(0,2)$$

 δ_g : Multiplicative fixed covariate effects for the increase or decrease in rate of progression for plasma NfL level, i.e., missing (g = 3) and high (g = 2) relative to low (g = 1) common across all visits

$$\delta_1 = 0; \ \delta_2 \sim Normal(0, 10^2); \ \delta_3 \sim Normal(0, 10^2)$$

 η_r : Multiplicative fixed covariate effects for the increase or decrease in rate of progression for regions, i.e., Japan (r = 2) relative to US (r = 1) common across all visits

$$\eta_1 = 0; \ \eta_2 \sim Normal(0, 10^2)$$

 σ_t : Measurement error per treatment arm

$$\sigma_t \sim Unif(0,10); t = 1,2$$

The θ_t parameters represent the multiplicative proportional slowing in rate of progression for treated relative to placebo (t=1); also referred to as the functional-impairment progression rate ratio (FPRR). For placebo, the FPRR is assumed to be 1 ($\theta_1 = 1$). Thus, the FPRR parameter for treatment (Lu AF82422) represents the multiplicative change to the mean progression of a placebo patient. If the FPRR is less than 1 then the progression for treatment t is slower than for placebo. A value of FPRR = 0.75 corresponds to a 25% slowing in progression and a value of 0.25 represents a 75% slowing in progression. The errors for the individual observations are modelled as independent normal distributions with a standard deviation of σ .

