In the case where patient i died prior to the Week 48 assessment, and patient j has not died prior to the Week 48 assessment:

•
$$u_{ij} = -1$$

In the case where patient i did not die prior to the Week 48 assessment, and patient j died prior to the Week 48 assessment:

• $u_{ij} = 1$

In the case where both patient i and patient j are alive at Week 48 assessment:

- $u_{ij} = -1$ when UMSARS score for patient i at Week 48 > UMSARS score for patient j at Week 48
- u_{ij} = 1 when UMSARS score for patient i at Week 48 < UMSARS score for patient j at Week 48
- u_{ij} = 0 when UMSARS score for patient i at Week 48 = UMSARS score for patient j at Week 48

Using the u_{ij} for every pair of patients defined above, a score is assigned to each subject, $U_i = \sum_{i \neq j} u_{ij}$.

A t-test is applied to the U_i scores to compare the treatment groups. The estimated mean difference and associated SE from each of these analyses will be combined using Rubin's Rule. The p-value from this combined analysis will be presented.

Assumptions of Primary Efficacy Model

The following analyses will be conducted to test the sensitivity of the results to the primary efficacy model assumptions:

- The Bayesian repeated measures primary analysis model will be explored for sensitivity to priors by using a sceptical alternative for θ_2 , i.e., using a PERT distribution with mode 1.1 and a shape of 7.44 corresponding to a prior that Lu AF82422 is doing 60% worse than placebo.
- The UMSARS TS will be analysed using a restricted maximum likelihood (REML)-based mixed model for repeated measures (MMRM). The model will include the following: region, CCI and treatment (Lu AF82422 and placebo) as fixed factors, baseline UMSARS TS as continuous covariate, treatment-by-week interaction and baseline UMSARS TS-by-week interaction. An unstructured covariance structure will be used to model the within-patient errors. The Kenward-Roger approximation will be used to estimate denominator degrees of freedom. The analysis will be performed using all available observations (observed cases [OC] data) in the DBP. The estimated treatment differences between Lu AF82422 and placebo obtained at Week 48 will be estimated based on the least squares means for the treatment-by-week interaction in the MMRM model. Estimated treatment differences at Week 60 and 72 will be exploratory. In case of issues converging, a Toeplitz structure will be fitted instead.

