20 Interim Analyses

No interim analyses will be conducted for this study.

21 Sample Size Considerations

The 18331A sample size has been selected to ensure an appropriate power to detect a 40% slowing in MSA progression in the Lu AF82422 CO dose group compared to the placebo group on a 5% significance level evaluated 1-sided. Applying a repeated measures model with proportional treatment effect, yields an approximate 75% power when having N=60 patients allocated 2:1 in favour of Lu AF82422 treatment (i.e., 40 on Lu AF82422 *versus* 20 on

Study 18331A - Statistical Analysis Plan

placebo) when using the NLMIXED procedure for simulating in SAS[®]. To account for differences in treatment duration due to the study design, approximately 50% of the patients are expected to contribute with 60 weeks data and 25% of the patients with full 72 weeks data. On top, an overall 20% drop-out rate has been accounted for. For comparison, it is expected that the frequentist repeated measures model used for simulation is quite similar in relation to performance to the primary Bayesian repeated measures model.

22 Statistical Software

The statistical software used will be SAS[®], version 9.4 or later, and R, version 3.12 or later, respectively. For R, the packages Jags and Coda would be required to run the MCMC procedures.

23 Changes to Analyses Specified in the Protocol

• According to SAP section 16.1.4, TEAEs will be assigned to two periods rather than four periods as described in Protocol section 16.10.1, the reason being that the safety follow up periods following the DBP and the OLEP, respectively, will be part of the reporting periods rather than individual periods. In this way the first safety follow up period following the DBP will be reported as part of the DBP, and the safety follow up period following the OLEP will be reported as part of the OLEP.

24 Details on Data Handling

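### The primary model has no term for the baseline error shared by all of a patient's change scores, and no baseline UMSARS term; this costs precision and can pull θ towards 1

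*SAP*

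**What the plan says.** SAP 14.3.1 describes the primary analysis as "Repeated measures for the change from baseline in the UMSARS TS score". The mean is written as zero plus the sum over 12-week intervals of (β_k + β_i) times exposure, all multiplied by θ and by exp(δ + η). Here β_i is a patient's single random slope, δ is the NfL category and η is region. On the residuals the section states: "The errors for the individual observations are modelled as independent normal distributions"; their SD may differ by arm. There is no subject intercept and no baseline UMSARS term.

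SAP 14.3.3 openly chooses a simple covariance structure and reports small bias and adequate type I error in the scenarios tried. It does not discuss error shared through the baseline.

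Other models in the SAP are built differently. The MMRM in 14.3.5 has "baseline UMSARS TS as continuous covariate", a baseline-by-week term and an unstructured covariance. The spline model in 14.3.5 is a constrained longitudinal analysis, also unstructured. The ANCOVA in 14.3.7 includes baseline UMSARS TS.

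SAP section 21 aims to "detect a 40% slowing in MSA progression" at a "5% significance level evaluated 1-sided". It says the model "yields an approximate 75% power when having N=60 patients" "allocated 2:1 in favour of Lu AF82422 treatment".

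**The concern.** Write the score at visit j as true score plus e_j, and the baseline as true score plus e_0. Each change score then contains −e_0, the same quantity at every visit. A random slope through the origin describes deviations that grow with time; it cannot describe one that is constant. The model therefore gives a patient's visits the wrong weights and puts part of e_0 into the slope.

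Two things follow.

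- **Precision.** Planned power is about 75% with 20 placebo patients, so there is little to give away.
- **The estimate of θ.** θ multiplies β_i as well as β_k, so the model requires the between-patient spread of slopes to shrink in proportion on active treatment. Baseline error does not shrink with treatment. Once it is absorbed into the slope term, the two arms' spreads look more alike than a true θ of 0.6 implies, which pulls θ towards 1.

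Omitting baseline UMSARS TS is a separate loss, to the extent that baseline severity predicts rate or the observed baseline carries error.

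**Working it through.** **Inputs from the documents (SAP section 21):** one-sided 5%, θ = 0.6, 40 against 20 patients, 20% drop-out, about half with 60 weeks of data and a quarter with 72. The remaining quarter is taken as 48 weeks.

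**Inputs not in the available text:** placebo rate, slope SD, score SD. Assumed ranges are 8 to 16 points per year and a single-score SD of 1.5 to 5, with baseline error equal to visit error.

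**The plan's 75%.** It cannot be reproduced, because it comes from a simulation whose variances are not given. As a consistency check on per-patient rates, 75% power needs 0.4 / (CV × √(1/40 + 1/20)) = 1.645 + 0.674 = 2.319, so CV = 0.63. With 32 against 16 patients (20% fully lost), CV = 0.56. The analytic step below fixes the total CV at 0.6, so that the SAP form has 75% power.

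**Step 1: error variance of one patient's slope.** Time t is in 12-week units, the mean is linear, and single-score variance is σ².

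- SAP weights (through the origin): σ² [1/Σt² + (Σt)²/(Σt²)²]
- Allowing for the shared error (GLS, n visits): σ² / [Σt² − (Σt)²/(n+1)]

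| Visits | Σt | Σt² | SAP form | GLS |
|---|---|---|---|---|
| 4 (Week 48) | 10 | 30 | 1/30 + 100/900 = 0.1444σ² | 1/(30 − 20) = 0.1000σ² |
| 5 (Week 60) | 15 | 55 | 1/55 + 225/3025 = 0.0926σ² | 1/(55 − 37.5) = 0.0571σ² |
| 6 (Week 72) | 21 | 91 | 1/91 + 441/8281 = 0.0642σ² | 1/(91 − 63) = 0.0357σ² |

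**Step 2: analytic power, five visits, 12 points per year.** The rate is 12 × 12/52 = 2.77 per 12 weeks, so total variance is (0.6 × 2.77)² = 2.76. Power after the change is Φ(2.319/√R − 1.645), where R is the ratio of new to old total variance.

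| Score SD | Error part, SAP → GLS | R | Power from 75% |
|---|---|---|---|
| 2 | 0.370 → 0.229 | 0.949 | 76.9% (+1.9) |
| 3 | 0.833 → 0.514 | 0.885 | 79.4% (+4.4) |
| 4 | 1.481 → 0.914 | 0.795 | 83.1% (+8.1) |

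Over the wider ranges the gain runs from +0.6 (16 per year, SD 1.5) to +14.3 (8 per year, SD 3.5). In the last cell the error part, 12.25 × 0.0926 = 1.13, is most of the total variance of (0.6 × 1.846)² = 1.23, so it is an extreme case.

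**Step 3: simulated power.** Maximum-likelihood fits, 650 to 700 trials per cell, θ also scaling the slope SD, arm-specific residual SD, 20% drop-out, linear mean, no NfL or region terms, no baseline–slope correlation. Each model was calibrated to one-sided 5%. Monte Carlo SE is about 1 to 2 points.

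| Rate per year, slope CV, score SD | SAP form | + subject intercept | Baseline as outcome |
|---|---|---|---|
| 12, 0.58, 2 | 95.1% | 96.9% | 97.0% |
| 12, 0.53, 3 | 87.6% | 94.0% | 94.7% |
| 12, 0.47, 4 | 76.1% | 88.3% | 89.9% |
| 10, 0.50, 3 | 81.3% | 90.6% | 91.3% |
| 14, 0.55, 3 | 92.4% | 95.4% | 96.4% |
| 12, 0.72, 3 | 86.6% | not run | 88.9% |
| 12, 1.0, 2 | 88.9% | not run | 90.6% |

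Type I error of the SAP form at nominal 5% was 4.0% to 5.1%. In the third row, baseline as an additive covariate alone gave 82.3%: +6.2 points, against +12.2 for the intercept.

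**Step 4: simulated θ.** True θ 0.60, 12 points per year, 300 trials per cell.

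- Score SD 3, slope SD 1.6 per 12 weeks: median θ 0.64 in the SAP form, 0.59 with an intercept.
- Score SD 4, slope SD 1.3: 0.68 against 0.59. Calibrated power in this smaller run was 69% against 88%. The slope CV is 1.3/2.77 = 0.47, so this is the third row of the table; the larger run is the better guide to power.

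A further run of 200 trials per cell gave median θ of 0.64 and 0.67 against about 0.60, and no loss when baseline error was set to zero.

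**The case against.** The strongest defence is that the simplicity is deliberate and disclosed, that type I error is controlled, and that the MMRM and the spline model already handle shared baseline error, for mUMSARS as well (SAP 14.4.1). The disclosure and the type I error control stand. But sensitivity models do not decide success; the posterior probability from the primary model does. The SAP's statement about small bias covers selected scenarios, and the available text does not say whether any of them included baseline error.

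Four stronger readings are tempting and are not supported:

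- **That a patient's change scores are treated as independent.** They are independent only given the random slope, which already correlates a patient's visits. What is missing is the constant component.
- **That the power loss is a known figure.** The placebo rate and SDs are not in the available text, so any single number is an assumption.
- **That chance baseline imbalance passes straight into θ.** Differences in level are subtracted out. Imbalance, with an SE of √(1/40 + 1/20) = 0.27 SD, matters only through baseline error or an association between baseline and rate.
- **That the Protocol shows such an association in these patients.** The sentence "There is a sigmoid progression of clinical impairment and deficits over time" (Protocol 2.1.1) describes the whole disease course. The same text puts patients diagnosed early, with low UMSARS, in the steep phase. Entry is limited to UMSARS Part I of 16 or less, and SAP 14.3.3 expects close to a straight line in earlier patients.

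It is also fair that putting an intercept and a baseline covariate in together has not been tested.

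**Conclusion.** The point holds as a matter of efficiency and of estimation under the alternative. It does not show invalid inference: the SAP form kept its type I error near 5%.

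If baseline error is similar to visit error, the cost is about 1 to 14 points of power, typically 2 to 8 at 12 points per year with score SD 2 to 4. Under a proportional effect, a true 40% slowing is then reported as about 32 to 36% in the settings simulated. If baseline error is negligible, there is no gain from the change and no material loss.

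The direction was the same in every setting with baseline error. The size is not established, because it rests on assumed variances and on likelihood approximations without the NfL and region terms.

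The missing intercept matters more than the missing covariate. A baseline–rate correlation of 0.2 to 0.4 would remove a further 4% to 16% of slope variance (0.2² to 0.4²), but that correlation is assumed, not documented.

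**What to change.** Before unblinding, in SAP 14.3.1:

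- Add a subject-level intercept b0_i ~ N(0, σ_0²) to μ_ij, multiplied neither by θ nor by the covariate terms. Modelling the baseline score as an outcome is an equivalent route.
- Separately, adjust for baseline UMSARS TS (baseline mUMSARS for the key secondary endpoint) as a centred multiplicative covariate on the rate, beside δ and η. If both changes are made, check by simulation that they work together: b0_i is essentially minus the baseline error, so it correlates with the observed baseline.
- Re-run the threshold calibration, the bias check and the power simulation with the sponsor's own variances, for each endpoint analysed with the Bayesian model. Include scenarios with and without baseline error.
- Align Protocol 17.9.2, which lists the features of the same model.

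The cost is one or two extra parameters and a calibration re-run across the Bayesian endpoints. If baseline error proves negligible, σ_0 shrinks towards zero and little is lost.

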14.3.2 Posterior Summaries

The Bayesian posterior distributions of all model parameters are calculated using Markov chain Monte Carlo (MCMC). The algorithm allows the generation of at least M = 100,000 draws from the joint posterior distribution for all model parameters. In particular, summaries of the Bayesian posterior distribution for the effect of Lu AF82422 compared to placebo, θ_2 , will be provided including the mean, median and 95% credible intervals together with the probability that the active dose is superior to placebo, $Pr(\theta_2 < 1)$. In addition, the probability of at least a 20% slowing effect will be presented, $Pr(\theta_2 < 0.7)$.

Finally, summaries of the Bayesian posterior distribution for the remaining model parameters will be provided including the mean, median and 95% credible intervals.

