#### 17.9.2 Primary Analysis of the Primary Endpoint(s)

The primary efficacy analysis of UMSARS TS following up to 72 weeks of treatment in the DBP will be based on a Bayesian repeated measures model of the change from baseline through up to 72 weeks. Thus, also defined as the estimator used for the primary estimand. The repeated measures model will be based on observed cases only (that is, no imputation) and incorporates the following features:

- Fixed effects for change in UMSARS TS progression per visit: 12, 24, 36, 48, 60, and 72 weeks
- Participant-level random effects for the rate of UMSARS progression across visits
- Fixed multiplicative treatment effect,  $\theta$ , for increase or decrease in the overall rate of UMSARS progression of Lu AF82422 relative to placebo common across all visits. In particular, if  $\theta$ <1, the active treatment slows the rate of progression of UMSARS relative to placebo. If  $\theta$ >1, the active treatment increases the rate of progression of UMSARS relative to placebo. If  $\theta$  = 1, the rate of progression of UMSARS is the same for both active treatment and placebo.
- Fixed multiplicative covariate effects in the increase or decrease in the overall rate of progression of UMSARS for and region (US and Japan) common across all visits
- Prior distribution for model parameters selected in a conservative and non-informative manner using relatively large outcome spaces

The Bayesian posterior distributions of all model parameters are calculated using Markov chain Monte Carlo (MCMC). The algorithm allows the generation of at least M=10,000 draws from the joint posterior distribution for all model parameters. In particular, summaries of the Bayesian posterior distribution for the treatment effect compared to placebo,  $\theta$ , will be provided including the mean, median and 95% credible intervals; the probability that Lu AF82422 is superior to placebo,  $Pr(\theta < 1)$ , which constitutes the primary analysis of the study; Additionally, the probability the treatment slows the rate of progression by at least 10%,  $Pr(\theta < .9)$ ; and the probability the treatment slows the rate of progression by at least 20%,  $Pr(\theta < .8)$ , will be provided.

Finally, summaries of the Bayesian posterior distribution for the remaining model parameters will be provided including the mean, median and 95% credible intervals.

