15.1 Calibrating primary analysis

The final analysis will use all available data on all enrolled participants at baseline through 48-72 weeks. A success threshold is defined for the final analysis to maintain an overall alpha of 5% evaluated one-sided. The effect of Lu AF82422 will be evaluated using a Bayesian posterior probability of superiority relative to placebo with a threshold of 97.5% identified through simulations.

Lu AF82422, CCI dose: $Pr(\theta_2 < 1) > .975;$

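### SAP 14.3.2 labels Pr(θ₂ < 0.7) as the probability of at least a 20% slowing; on the SAP's own scale it is the probability of at least 30%

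*SAP*

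**What the plan says.** SAP 14.3.2 lists what will be reported from the posterior of θ₂, the progression rate ratio of Lu AF82422 to placebo: mean, median, 95% credible interval and Pr(θ₂ < 1). It then adds one effect-size probability: "In addition, the probability of at least a 20% slowing effect will be presented", written as Pr(θ₂ < 0.7).

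SAP 14.3.1 fixes the scale on which slowing is measured: "A value of FPRR = 0.75 corresponds to a 25% slowing in progression". It adds that a ratio of 0.25 is a 75% slowing.

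Protocol 17.9.2 plans two such summaries. One is "the probability the treatment slows the rate of progression by at least 10" percent, with Pr(θ < .9). The other is "the probability the treatment slows the rate of progression by at least 20" percent, with Pr(θ < .8).

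SAP section 23, which lists changes from the protocol, has a single entry, on adverse events: "TEAEs will be assigned to two periods rather than four periods". It says nothing about these summaries.

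**The concern.** The words and the formula in the SAP sentence describe different events. A reader of the report would take the number as the chance that the drug slows progression by a fifth or more, when the formula gives the chance that it slows progression by three tenths or more.

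This is the only effect-size probability that SAP 14.3.2 names beyond Pr(θ₂ < 1). SAP 14.3.3 gives interpretable posterior probabilities, and an effect expressed as percentage slowing, among its reasons for choosing this model. In a phase II trial of 60 patients, such a probability is a natural figure to use when judging whether an effect is large enough to pursue. If the text is followed, the error makes the drug look less likely to achieve a 20% slowing than the data support.

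A smaller, separate point is that SAP 14.3.2 does not mention the protocol's 10% summary.

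**Working it through.** **1. The scale.** Take slowing = 1 − θ and test it on every pair in the documents.

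| Source | θ | 1 − θ | Stated slowing | Match |
|---|---|---|---|---|
| SAP 14.3.1 | 0.75 | 0.25 | 25% | yes |
| SAP 14.3.1 | 0.25 | 0.75 | 75% | yes |
| Protocol 17.9.2 | 0.9 | 0.10 | 10% | yes |
| Protocol 17.9.2 | 0.8 | 0.20 | 20% | yes |
| SAP 14.3.2 | 0.7 | 0.30 | 20% | **no** |

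Other scales do not rescue the pairing. With 1/θ − 1, θ = 0.7 gives 42.9%, and 20% needs θ = 0.833. With −ln θ, θ = 0.7 gives 35.7%, and 20% needs θ = 0.819.

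**2. Direction.** The event θ₂ < 0.7 lies inside the event θ₂ < 0.8. So Pr(θ₂ < 0.7) ≤ Pr(θ₂ < 0.8) for any posterior, and it is strictly smaller whenever there is posterior mass between 0.7 and 0.8. This needs no assumption.

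**3. Size (illustration).** The documents give no posterior, so its shape and spread are assumed here. Take ln θ₂ as normal. Back out its standard deviation from SAP section 21, where the design "yields an approximate 75% power when having N=60 patients" for a 40% slowing (θ = 0.6):

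log-SD = −ln(0.6) / (z_α + z_0.75)

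- z_α = 1.645: 0.5108 / (1.645 + 0.6745) = 0.220
- z_α = 1.960: 0.5108 / (1.960 + 0.6745) = 0.194

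Both values are used because SAP 14.2 targets one-sided 5%, while SAP 15.1 sets the posterior cut-off "with a threshold of 97.5% identified through simulations".

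For posterior median m, Pr(θ₂ < c) = Φ(ln(c/m) / log-SD).

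| m | log-SD | Pr(< 0.8) | Pr(< 0.7) | Gap |
|---|---|---|---|---|
| 0.60 | 0.220 | 0.904 | 0.758 | 0.146 |
| 0.60 | 0.194 | 0.931 | 0.787 | 0.144 |
| 0.70 | 0.220 | 0.728 | 0.500 | 0.228 |
| 0.70 | 0.194 | 0.754 | 0.500 | 0.254 |
| 0.75 | 0.220 | 0.615 | 0.377 | 0.238 |
| 0.75 | 0.194 | 0.630 | 0.361 | 0.269 |
| 0.80 | 0.220 | 0.500 | 0.272 | 0.228 |
| 0.80 | 0.194 | 0.500 | 0.246 | 0.254 |

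**4. A result that only just succeeds.** If Pr(θ₂ < 1) = 0.975, then m = exp(−1.96 × log-SD).

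- log-SD 0.220: m = 0.649, giving 0.828 against 0.633.
- log-SD 0.194: m = 0.684, giving 0.791 against 0.548.
- If the 0.975 cut-off is taken to be equivalent to one-sided 5%, as the SAP says, the posterior log-SD is 1.645 × 0.220 / 1.96 = 0.185. Then m = 0.696, giving 0.774 against 0.512.

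**5. Check with another shape.** With a normal posterior on the θ scale, the SD implied by 75% power is 0.4 / (1.645 + 0.6745) = 0.172 or 0.4 / (1.960 + 0.6745) = 0.152. The gap over medians 0.60 to 0.80 is then 16 to 26 points.

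**The case against.** The strongest reply has five parts.

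- **Which element is wrong is unknown.** The text shows that label and threshold disagree, not which was intended. If 0.7 was meant, the computed quantity is sound and only the label is wrong. This stands, so the understatement is conditional on Pr(θ₂ < 0.7) being computed and reported as 20%. The R code in SAP Appendix III is redacted, so the programmed threshold cannot be seen.
- **No decision depends on it.** Success is Pr(θ₂ < 1) > 0.975, and both steps of the fixed sequence use that criterion. This also stands, and it limits the matter to a supplementary summary.
- **Silence in section 23 is weak evidence of intent.** Other differences from the protocol are not listed there either: the MCMC draws rise from 10,000 to 100,000, and the diary-fall model changes from negative binomial to MMRM. That is fair, but it does not repair the contradiction, which lies within the SAP itself.
- **The sizes rest on an assumed posterior.** They do. The log-SD comes from a frequentist power statement, and using 0.220 with a 1.96 cut-off implies about 64% power rather than 75%. The consistent value, 0.185, leaves a gap of 26 points at bare success (0.774 − 0.512). The gap is smaller away from the middle range: about 3 to 5 points at a median of 0.50 and 9 to 10 points at 1.0.
- **The 10% summary may not have been dropped.** The list in 14.3.2 is not worded as exhaustive, so that omission is only a question to settle.

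**Conclusion.** The concern holds. By the SAP's own definition, θ₂ < 0.7 is a slowing of at least 30%, and the 20% label belongs with θ₂ < 0.8, as in the protocol. That follows from the text alone. If the SAP is followed as written, a pre-specified summary of the primary endpoint will carry the wrong label and cannot overstate the probability of a 20% effect.

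The size depends on the posterior. Under the log-normal illustration the shortfall is 14 to 27 percentage points for medians of 0.60 to 0.80. For a result that just meets the success threshold, about 0.51 to 0.63 would be shown in place of 0.77 to 0.83.

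The primary and key secondary tests, their threshold, the sample size, and the posterior mean, median and credible interval do not change.

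**What to change.** Before unblinding, make the label and the threshold in SAP 14.3.2 agree.

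- **Default, matching the protocol:** report Pr(θ₂ < 0.8) as the probability of at least a 20% slowing, and restore Pr(θ₂ < 0.9) for 10%.
- **If 0.7 was intended:** label it as at least a 30% slowing, and record in section 23 both that change and any protocol summary that is dropped.

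In either case, confirm that the analysis program and the table shells use the threshold given in the text. Choosing between 0.7 and 0.8 after the results are known would look data-driven.

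The cost is one number or one label, a line in section 23 if the change was deliberate, and a program check. No new data or analysis is needed.
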